3.6.6 Risk groups

Risk groups will consist of those patients with specific chronic conditions (e.g., immunocompromised), long-term care facility residents, and the elderly. A specific categorisation of risk groups will be provided in the SAP.

3.7 SARI patient identification

Hospitalised SARI patients will be identified based on the defined SARI definition (3.6.2). Depending on the Study Contributor, the SARI patient's point of identification will be different (e.g., during consultation in the emergency department (ED), or at admission to infectious disease or internal medicine ward). For every participating study site, the patient flow will be documented in detail.

3.8 Pathogens of interest and laboratory testing

3.8.1 Pathogens of interest

The pathogens of interest are as follows:

- Severe Acute Respiratory Syndrome Coronavirus-2 (SARS-CoV-2)
- Influenza
 - Influenza A
 - A-H1
 - A-H3
 - o Influenza B
- Respiratory Syncytial Virus (RSV)
 - RSV A and RSV B
- Parainfluenza
 - Type 1-4
- Human Metapneumovirus (hMPV)
- Human Rhinovirus (HRV)
- Human Enterovirus (HEV)
- Adenovirus
- Human coronavirus
 - Types 229E, NL63, OC43 and HKU1

At minimum, sites should have testing capacity for SARS-CoV-2, Influenza A and B, and RSV A and B. Additional pathogens may be added to the study depending on epidemiological trends (e.g., inclusion of an emerging pathogen).

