3.4 Study period

From June 2024, with a minimum duration of 12 months and an expected duration of two years. A graphical visualisation of the study timelines is provided in the figure below (Figure 1):

Figure 1: Study timelines

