Universitäts-klinikum Ulm,	SeeGene / GeneXpert	ТВС	
Germany			

Table 2. Multiplex assays (brand, panel, and number of pathogens) used by Study Contributors

Study Contributor, Country	Brand	Panel	Number of pathogens tested
Universitäts-klinikum Freiburg,	Pathofinder	Respifinder 2smart	18
Germany			

*CIRI-IT location Rome does not use multiplex yet, but is considering implementation of SeeGene Allplex or Roche ePlex (to be finalised in June 2024); TBC, to be confirmed

Further genotyping or subtyping will be performed on specimens that test-positive for:

- RSV:
 - Subtype A and B (if not available through local multiplex)
- Influenza:
 - Type A and B (if not available through local multiplex)
 - Subtypes A H1, Influenza A H3 (if not available through local multiplex)
- SARS-CoV-2:
 - Genotyping (pangolin lineage)

Genomic sequencing will be performed by whole genome sequencing or next generation sequencing using commercially available molecular kits. Sites will be requested to communicate to the Study Team the sequencing methodology applied, software version used, and the references of the laboratory performing the test.

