3.13.2 Total SARI and pathogen-specific SARI numbers

The total number and proportion of positive laboratory samples for each respiratory pathogen of interest (see section 3.8.1) and co-infections (see section 3.6.4) will be provided. Counts and proportions (%, along with 95% exact binomial confidence intervals) will be provided by calendar time, by Study Contributor, by country and by age- and risk groups of interest. Co-infections (%) will be described, by number of pathogens, by pathogen type and by healthcare utilisation outcomes. Visualisations of these counts and percentages over time will be provided.

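### The co-infection proportion is tracked over calendar time without a fixed set of viruses, so it can rise because more targets are tested

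*Protocol*

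**What the plan says.** - **Pathogen list (3.8.1).** The list is open: "Additional pathogens may be added to the study depending on epidemiological trends (e.g., inclusion of an emerging pathogen". The floor is "At minimum, sites should have testing capacity for SARS-CoV-2, Influenza A and B, and RSV A and B". Section 3.8.2 makes the remaining viruses preferred, not required.
- **Panels (3.8.2, Table 2).** Several panels are marked as to be confirmed. The table footnote adds: "CIRI-IT location Rome does not use multiplex yet, but is considering implementation of SeeGene Allplex or Roche ePlex (to be finalised in June 2024". June 2024 is also the month data collection starts.
- **Duration and sites (3.4, 3.2).** The study runs "From June 2024, with a minimum duration of 12 months and an expected duration of two years". Countries and Study Contributors may be added during that time.
- **Co-infection (3.6.4).** It is two or more laboratory-confirmed infections on respiratory samples in the accepted window. No common panel is required.
- **Output (3.13.2).** The section covers "The total number and proportion of positive laboratory samples for each respiratory pathogen of interest" and also co-infections. On their presentation it says: "Counts and proportions (%, along with 95% exact binomial confidence intervals) will be provided by calendar time". Plots over time are planned, and results are also given by Study Contributor and by country.
- **Limitations (5).** Assay differences are acknowledged for comparisons across sites and with other surveillance systems. Change of panel within the study is not mentioned.

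**The concern.** A count of two or more detections depends on how many targets are looked for. Each added target gives every patient who already has one detection a further chance of being counted as co-infected. With true epidemiology constant, the co-infection proportion rises on the date a pathogen is added or a site moves to a wider panel.

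Co-infection prevalence is the secondary objective, and the research aim is to monitor virological and clinical trends. A step produced by the testing repertoire would sit in the same plot as a real change, and the protocol gives no rule for telling them apart. Using only samples tested for a given virus as its denominator deals with that virus's own positivity. It does not remove the step in co-infection, which combines viruses.

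**Working it through.** **Reproducing the plan's own figures.** The hospitals in Table 1 sum to 22. Then 22 × 300 = 6,600, and 6,600 × 0.9 = 5,940. Exact binomial half-widths, (upper − lower)/2 at n = 5,940, are 1.0255 points at 20%, 1.1094 at 25%, 0.3651 at 2%, 0.6575 at 7% and 0.8349 at 12%. These agree with Table 4 to within rounding in the third decimal. Table 4 is sound and is used below only as a source of prevalences.

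**Inputs.**
- Mandatory viruses, Table 4 minimum: 20%, 2%, 7%. Maximum: 25%, 7%, 12% (SARS-CoV-2, RSV, influenza).
- Assumed, not in the protocol: viruses occur independently; an added pathogen has prevalence q of 1% to 5%; the six non-mandatory groups (adenovirus, parainfluenza, hMPV, HRV, HEV, human coronaviruses) have 1% to 3% each; hospitals are of equal size.

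**Baseline, three viruses.** P(none) = Π(1 − p). P(exactly one) = P(none) × Σ p/(1 − p). Co-infection = 1 − P(none) − P(exactly one).
- Minimum: P(none) = 0.80 × 0.98 × 0.93 = 0.7291; P(exactly one) = 0.2520; co-infection = 0.0188, or 1.9%.
- Maximum: P(none) = 0.75 × 0.93 × 0.88 = 0.6138; P(exactly one) = 0.3345; co-infection = 0.0517, or 5.2%.

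**One pathogen added at all sites.** The increase is q × P(exactly one).

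| q | Minimum, from 1.9% | Maximum, from 5.2% |
|---|---|---|
| 1% | 2.1% | 5.5% |
| 3% | 2.6% | 6.2% |
| 5% | 3.1% | 6.8% |

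**Could such a step pass for a real change?** Suppose the 5,940 patients split evenly, 2,970 before and 2,970 after, with q = 5%.
- Minimum: difference 0.0126; standard error √[(0.0188 × 0.9812 + 0.0314 × 0.9686)/2,970] = 0.0041; ratio about 3.1.
- Maximum: difference 0.0167; standard error √[(0.0517 × 0.9483 + 0.0684 × 0.9316)/2,970] = 0.0062; ratio about 2.7.
- At q = 1% the ratios are about 0.7 and 0.6, so the step would not stand out.

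In a single month, with 5,940/12 = 495 patients, the exact 95% interval around 3% is about 1.7% to 4.9%. Month-to-month noise hides a step of this size; a comparison of longer periods does not.

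**One hospital moving from three viruses to all nine groups.**
- Minimum: 1.9% to 3.5–7.0% at that hospital, a rise of 1.6 to 5.1 points.
- Maximum: 5.2% to 7.2–11.5%, a rise of 2.0 to 6.4 points.
- Pooled over 22 hospitals (divide by 22): 0.07 to 0.29 points.

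**After the fix.** On the three mandatory viruses alone, expected co-infection stays at 1.9% or 5.2% whatever is added and whenever.

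**The case against.** The strongest reply is that panel restrictions, start dates and figure annotation belong in the SAP, which is not shown, and that no addition is scheduled. Section 6.6 requires protocol changes to be documented in amendments, where a start date could be set. Assay and sampling date are collected, and co-infections are broken down by pathogen type and by Study Contributor, so an artefact could be traced. Much of this stands, and it is why the point is minor. It does not remove the point. The protocol itself fixes a panel-dependent definition and commits to showing it over time, and an amendment that adds a pathogen would not by itself change that output.

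A reader might infer more than the documents support:

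- **That positivity in general steps up.** SARS-CoV-2, influenza and RSV are required at every site from the start and are unaffected. For other viruses an artificial step arises only if untested samples stay in the denominator, which 3.13.2 leaves open.
- **That pathogens enter because they are already rising.** The text ties additions to epidemiological trends and gives an emerging pathogen as an example. It states no rule that prevalence must be rising.
- **That the Rome hospital will switch mid-study.** It is only considering multiplex. The document gives a decision date, not a start date for testing.
- **That an any-virus-detected trend is distorted.** No such output is planned.
- **That an added pathogen's surge would be reported as a full-period proportion.** The protocol specifies no such labelling.

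**Conclusion.** The point holds in limited form and is minor. The calendar-time co-infection series rests on a set of viruses that may change, and neither the analysis section nor the limitations section deals with change within the study. The step for a network-wide addition is about 0.3 to 1.7 points. At the upper end it could pass for a real change between two halves of the study; at the lower end it would not be noticeable. A panel change at one hospital is negligible in the pooled series and matters only in that hospital's own series.

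These sizes rest on independence between viruses, on Table 4 for the three mandatory ones, and on assumed prevalences for all others. The direction does not depend on them: testing more targets cannot lower the count of patients with two or more detections.

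**What to change.** In section 3.13.2, state that:

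1. Calendar-time trends in co-infection use a fixed set of viruses tested throughout: SARS-CoV-2, influenza and RSV at all sites, and the full 3.8.1 list only for patients or site-months whose recorded assay covers it.
2. Each pathogen's positivity uses only samples tested for that pathogen.
3. A pathogen added during the study is reported from its introduction date and labelled with that period.
4. Co-infection on all targets may be shown separately, without a trend claim.

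In section 5, add change of panel within the study as a limitation.

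The cost is a few sentences and one more trend line. Assay used and sampling date are already in the minimum dataset, so no new data are needed. The drawback is that the fixed-set trend counts fewer viruses and so shows a lower level of co-infection.

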3.8.2 Laboratory testing

To the extent possible, clinical specimens will be collected from the patients eligible for the study as part of routine clinical sampling for diagnostic work-up. However, depending on local practice, additional sampling for the purpose of the study may be required. Samples collected between 14 days prior to and up to 72 hours after admission are accepted. Nasopharyngeal or oropharyngeal swabs are recommended. Additional respiratory specimens are accepted (e.g., nasal swabs, oropharyngeal swab, saliva, mouth wash, bronchoalveolar lavage, aspirates). Sample type will be recorded.

The specimens will be tested within the local laboratory infrastructures of the participating Study Contributors, for at least SARS-CoV-2, influenza A/B and RSV A/B, and preferably also for adenovirus,

Confidential Version 1.0 21 March 2024 Page **28** of **49** Parainfluenza 1-4, human metapneumovirus (hMPV), human rhinovirus (HRV), human enterovirus (HEV), and human coronaviruses (229E/NL63/OC43/HKU1), by using validated RT-PCR or multiplex RT-PCR assays, or another RNA amplification system with at least the same sensitivity as RT-PCR (e.g., transcription-mediated amplification (TMA)). Assays used are either commercial assays with known high sensitivity, specificity and/or concordance, or in-house developed assays that have undergone quality and/or validation processes. Study Contributors will be requested to submit validation logs (summarising the quality check process, results, timing and certificates of analysis for assays performed) to the Study Team.

			Number of pathogens
Study Contributor, Country	Brand	Panel	tested
VAHNSI,	In-house	In-house	20
Spain			
Val d'Hebron,	SeeGene	Allplex RP 1-3	19
Spain	Cepheid GeneExpert	Xpert [®] Xpress CoV-	4
		2/FLU/RSV plus	
GHTiP,	SeeGene	Allplex SARS-CoV-	4
Spain		2/FLU/RSV	19
		Allplex RP 1-3	
Hospital Clínico Universitario de	BioFire	FilmArray	18
Santiago de Compostela,			
Spain			
Hospital Clínic de Barcelona,	GeneXpert	ТВС	
Spain			
Hospital Universitario La Paz,	BioFire	ТВС	
Spain	Cepheid GeneXpert		
CIRI-IT,	SeeGene (Bari, Genoa)	Allplex RP 1-3	19
Italy	In-house (Milan)		
	TBC (Sienna, Pisa)		
Luigi Sacco Hospital,	SeeGene	Allplex RP	21
Italy			
UZA,	Pathofinder	Respifinder 2smart	18
Belgium			
St Pierre,	Qiagen Qiastat	RP SARS-CoV-2	18
Belgium	Abbott Alinity m RESP		4
	4-plex TaqMan	In-house	17
Universitäts-klinikum Frankfurt,	SeeGene	Allplex RP 1-3	19
Germany	BioFire	FilmArray RP2.1	18
Universitäts-klinikum Ulm,	SeeGene / GeneXpert	ТВС	
Germany			

Table 2. Multiplex assays (brand, panel, and number of pathogens) used by Study Contributors

Study Contributor, Country	Brand	Panel	Number of pathogens tested
Universitäts-klinikum Freiburg,	Pathofinder	Respifinder 2smart	18
Germany			

*CIRI-IT location Rome does not use multiplex yet, but is considering implementation of SeeGene Allplex or Roche ePlex (to be finalised in June 2024); TBC, to be confirmed

Further genotyping or subtyping will be performed on specimens that test-positive for:

- RSV:
 - Subtype A and B (if not available through local multiplex)
- Influenza:
 - Type A and B (if not available through local multiplex)
 - Subtypes A H1, Influenza A H3 (if not available through local multiplex)
- SARS-CoV-2:
 - Genotyping (pangolin lineage)

Genomic sequencing will be performed by whole genome sequencing or next generation sequencing using commercially available molecular kits. Sites will be requested to communicate to the Study Team the sequencing methodology applied, software version used, and the references of the laboratory performing the test.

3.9 Covariates and healthcare use

The complete dataset can be found in the id.DRIVE Common dataset case report form and is summarised in Table 3.

Cov	variate	Description
Age	e at hospital admission	Years, calculated based on date of birth and date of admission
Ger	nder assigned at birth	Male, female
Chr	onic conditions*	
	Asthma	Binary, if yes subcategory: Mild intermittent, Mild persistent,
		Moderate persistent, Severe persistent, No information
	Lung disease	Binary, if yes subcategory COPD and stage (Gold I – IV, no
		information)
Cardiovascular disease		Binary, if yes subcategory Congestive heart failure
Hypertension		Binary
	Chronic liver disease	Binary, if yes subcategory end stage liver disease (ESLD): No,
		Yes, No information
	Chronic renal disease	Binary, if yes subcategory end stage kidney disease (ESKD): no,
		yes but without dialysis, yes and on dialysis, No information.
	Diabetes type I	Binary
	Diabetes type II	Binary

Table 3. Study covariates and healthcare use

Covariate		Description
Obesity		Binary
Cancer		Binary. If yes, specification of subcategories: solid tumour,
		haematological cancer, no information. If solid tumour or
		haematological cancer is yes, further specification of cancer
		type to be selected from list.
Immunodeficier	ncy (or	Binary. If yes, specification of subcategories: Solid organ or
organ transplan	t)	islets transplant, Haematopoietic stem cell transplantation,
		Primary immunodeficiency, Advanced or untreated HIV
		infection, latrogenic immunodeficiency, other. If yes solid
		organ or islets transplant, specification of subcategories:
		Kidney, Liver, Intestines, Heart, Lung, Pancreas, Other, No
		information
Neurological dis	sorders	Binary
Pregnancy		Binary. If yes, specification of trimester: first, second, third
Body mass index (BN	/II)	Continuous
Smoking history		Never smoker, ex-smoker, occasional smoker, daily smoker,
		no information
Vaccination history i	nfluenza	Vaccination details of Influenza vaccination within 12 months
last 12 months		prior to SARI hospital admission, date, brand
Vaccination history	COVID-19	Vaccination history of COVID-19 vaccinations, date, brand
Vaccination history I	RSV	Vaccination history of RSV vaccinations, date, brand
Vaccination pneumo	coccus	Vaccination details of any pneumococcal vaccination, date,
		brand
Previous SARI hospit	alisation	Binary
in last 12 months		
Time since previous	SARI	<14 days, 14 days-3 months, >3 months, No information
hospitalisation		
Time between symp	tom	Days, continuous
onset and hospitalis	ation	
Long-term care facili	ty	Binary, if no, specification of residential situation before
residence [§]		hospitalisation: Home, Home with nursing care, Transfer from
		another hospital, Rehabilitation centre, Nursing home, other,
		no information
Respiratory support		None, oxygen therapy, non-invasive ventilation, mechanical
		ventilation, extra corporeal membrane oxygenation (ECMO),
		other
Cumulative number	of days of	Days, continuous
non-invasive ventila	tion,	
invasive ventilation,	or ECMO	
Length of hospital st	ау	Days, continuous
Admission to ICU		Binary
Length of ICU stay		Days, continuous
In-hospital death		Binary

Covariate	Description
Post-discharge destination	Home, Home with nursing care, Transfer to another hospital,
	Rehabilitation centre, Nursing home or other long-term care
	facility, Other
Treatments received during	Antibiotics, Antiviral drug(s), Corticosteroid(s), Immune-
hospital stay for the	modulator(s), Anti-SARS-CoV-2 antibodies, Other monoclonal
management of SARI episode	antibodies, None of the above.
	Brand name if anti-SARS-CoV-2 antibodies received during
	hospital stay
Treatments received prior to	Antibiotics, Antiviral drug(s), Corticosteroid(s), Immune-
hospital admission for the	modulator(s), Anti-SARS-CoV-2 antibodies, Other monoclonal
management of current SARI	antibodies, None of the above.
episode	Brand name if anti-SARS-CoV-2 antibodies received during
	hospital stay
Medicinal product for the	Binary. If yes, type (Antiviral drug,
prevention of SARS-CoV-2	Anti-SARS-CoV-2 antibodies, Other), brand and date
(pre- or post-exposure	(month/year) if SARS-CoV-2 monoclonal antibody
prophylaxis) in the 12 months	
prior to current	
hospitalisation	
Medicinal products for the	Binary. If yes, type (Antiviral drug,
prevention of RSV infection	Anti-RSV antibodies, Other), brand and date (month/year) if
within 12 months prior to	RSV monoclonal antibody
current hospitalisation	

*Definitions for each chronic conditions are specified in the id.DRIVE Common dataset case report form

§ At VAHNSI, long-term care facility residents are excluded

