3. To investigate the prevalence of co-infection with the viral respiratory pathogens of interest¹, in adult patients hospitalised with SARI, and the impact on healthcare utilisation outcomes².

² Healthcare utilisation outcomes are defined by outcome (hospitalisation without ICU admission or in-hospital death; ICU admission without in-hospital death; in-hospital death), by the need for respiratory support (none; non-invasive ventilation; mechanical ventilation; ECMO), discharge destination and length of stay.

Version 1.0

¹ SARS-CoV-2 and/or SARS-CoV-2 specific variant, Influenza A/B, Respiratory Syncytial Virus (RSV) A/B, Adenovirus, Parainfluenza viruses (1-4), human metapneumovirus (hMPV), human rhinovirus (HRV), human enterovirus (HEV), human coronaviruses (229E/NL63/OC43/HKU1)

Exploratory objectives are:

- 4. To calculate pathogen-specific SARI incidences and describe trends in adults (by time period, country, and level of severity);
- 5. To perform feasibility assessments for future respiratory disease studies within the id.DRIVE Study Network (e.g., effectiveness studies, impact studies).

Study methods

Study design: SARI-based surveillance study.

Data sources: A combination of primary and secondary data sources.

Data collection: Prospective

Study duration: From June 2024, with a minimum duration of 12 months.

Countries: The study will be conducted in Belgium, Spain, Italy, and Germany. Additional countries may be included during the study period.

Study participants: Adults (18 years and older) presenting at the participating hospitals during the study period who 1) are hospitalised and meet the SARI case definition AND who 2) meet the following criteria for:

- Inclusion: Willing and able to provide informed consent, when applicable, obtained from the patient or from the patient's Legally Acceptable Representative(s) (LAR)
- Exclusion: No exclusion criteria have been defined.

SARI case definition: A SARI case is defined as a hospitalised person with a suspicion of a respiratory infection with at least one of the following symptoms:

- cough
- fever (≥ 38 C°)
- shortness of breath
- sudden onset of anosmia, ageusia, or dysgeusia

with symptom onset within the last 14 days prior to hospital admission. This SARI definition is modified from the latest European Centre for Disease Prevention and Control (ECDC) case definition (specifying "suspicion of respiratory infection") [3].

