3.3.2 Exclusion criteria

No exclusion criteria have been defined.

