3.6.5.2 Discharge destination

Destination at hospital discharge will be specified using the following categories:

- Home
- Home with nursing care
- Transfer to another hospital
- Rehabilitation centre
- Nursing home or other long-term care facility
- Other
- No information

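### The protocol declares no exclusion criteria but leaves long-term-care residents out at VAHNSI (5 of 22 hospitals), so the pooled and Spanish count and share of residents will be too low

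*Protocol*

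**What the plan says.** On eligibility, Section 3.3.2 reads "No exclusion criteria have been defined", and the abstract's description of study participants repeats it. The only inclusion criterion in Section 3.3.1 concerns consent. The footnote to Table 3 in Section 3.9, a table of covariates, then says "At VAHNSI, long-term care facility residents are excluded". The restriction does not appear in the study population section, in the list of contributors (Table 1) or in the limitations (Section 5).

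On reporting, Section 3.6.6 states: "Risk groups will consist of those patients with specific chronic conditions (e.g., immunocompromised), long-term care facility residents, and the elderly". Section 3.13.2 promises counts and positivity "by Study Contributor, by country and by age- and risk groups of interest". Section 3.13.3 lists long-term-care residence among the characteristics to be tabulated, overall and by pathogen.

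On coding, Table 3 records long-term-care residence as yes or no. Only after a 'no' does it ask where the patient lived, with options that include "another hospital, Rehabilitation centre, Nursing home, other". The discharge list in Section 3.6.5.2 has the category "Nursing home or other long-term care facility", which treats a nursing home as one kind of long-term care facility.

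**The concern.** The eligibility statements cannot all be true. A reader of Section 3.3 would conclude that residents are enrolled everywhere, and would read a low share in Spain, or at VAHNSI, as a finding about patients rather than a consequence of who was allowed in.

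What is at stake is the description of a group the study sets out to describe under its second primary objective. VAHNSI patients contribute nothing to the count of residents but would count in full in the pooled and Spanish denominators. A comparison of Spain with the other countries would partly measure this restriction.

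The residence coding could push the same figure down further. If a site takes Table 3 literally, a nursing-home patient can be entered as not living in long-term care.

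**Working it through.** **Inputs.** Hospital and bed counts come from Table 1; 300 patients per hospital and 10% drop-off come from Section 3.10. The protocol does not give the true share of residents among SARI patients, L, so L is assumed to be 5% to 30% and equal across hospitals.

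**Reproducing the plan's figures.** Table 1 gives 5+1+1+1+1+1 = 10 hospitals in Spain, 6+1 = 7 in Italy, 2 in Belgium and 3 in Germany, 22 in all. Then 22 × 300 = 6,600, and 6,600 × 0.9 = 5,940. Both match Section 3.10.

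**Weight of VAHNSI.**
- Hospitals and planned patients: 5/22 = 22.7%; 5 × 270 = 1,350 of 5,940.
- Spain: 5/10 = 50% of hospitals.
- Beds: 3,347/20,646 = 16.2% overall; 3,347/8,881 = 37.7% in Spain.

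**Effect on the share of residents.** Let w be VAHNSI's weight.
- If VAHNSI still fills its quota with non-residents, the observed share is L(1 − w).
- If excluded residents are not replaced, it is L(1 − w)/(1 − wL).

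With equal enrolment per hospital (w = 5/22 pooled, 5/10 in Spain):

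| True share L | Pooled, quota filled | Pooled, not replaced | Spain, quota filled | Spain, not replaced |
|---|---|---|---|---|
| 5% | 3.9% | 3.9% | 2.5% | 2.6% |
| 10% | 7.7% | 7.9% | 5.0% | 5.3% |
| 20% | 15.5% | 16.2% | 10.0% | 11.1% |
| 30% | 23.2% | 24.9% | 15.0% | 17.6% |

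The relative shortfall, pooled, is 22.7% with the quota filled and 17.1% to 21.8% without replacement. For Spain it is 50% with the quota filled; without replacement it runs from 1 − 17.65/30 = 41% (L = 30%) to 1 − 2.56/5 = 49% (L = 5%).

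**Sensitivity to the weight.** If enrolment followed beds instead, w = 0.162 pooled and 0.377 in Spain. With the quota filled, the shortfall equals w: 16.2% and 37.7%. Without replacement at L = 30% it is 1 − 0.838/(1 − 0.162 × 0.30) = 12% pooled and 1 − 0.623/(1 − 0.377 × 0.30) = 30% in Spain.

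**Effect on positivity among residents.** Here residents are the denominator, so VAHNSI drops out of both parts of the fraction. The target is (5 × VAHNSI positivity + 17 × positivity elsewhere)/22; what is observed is positivity elsewhere. With 10% elsewhere:
- VAHNSI 10%: target 10.0%, bias 0.
- VAHNSI 5%: target 8.9%, bias +1.1 points.
- VAHNSI 15%: target 11.1%, bias −1.1 points.

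**Possible effect of the residence coding.** If a fraction m of enrolled residents is entered as 'no' with nursing home as prior residence, the pooled share (quota filled) becomes L × 17/22 × (1 − m). For L = 10% this is 7.7% at m = 0, 5.8% at m = 0.25 and 3.9% at m = 0.5. The value of m is unknown and may be zero.

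**The case against.** Several counter-arguments have weight.

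- **Scope of the bias.** A reader might infer that every long-term-care result is biased low. The protocol does not support that. The risk-group output in Section 3.13.2 is positivity within the group, which shifts only if VAHNSI's residents differ from residents elsewhere, and then in either direction. Only the count and share of residents are pushed down.
- **Nursing-home coding.** A reader might also infer that nursing-home residents are in fact recorded as non-residents. That is possible but not shown. Section 3.9 says Table 3 summarises a case report form that is not part of the protocol, and the form may define long-term care so that nursing homes are answered 'yes'. Nursing home is recorded as its own option, so such patients could be reclassified. Section 3.6.6 leaves the detailed risk-group categories to the SAP. What stands is that two lists in the protocol disagree.
- **Contaminated comparisons.** Section 3.13.4 does not name long-term-care residence among its example risk factors or its strata, so the protocol sets up no explicit resident versus non-resident contrast.
- **Incidence.** Incidence is exploratory, and Section 3.13.5 withholds it unless denominators can be mapped and missed SARI events accurately identified. Distorted VAHNSI incidence in older adults is therefore a risk, not a demonstrated error. The risk is real, because the catchment would be built from bed share and official age and gender distributions, which include residents. The screening logs in Section 4.3 carry only age group and gender, and the protocol does not say whether they count excluded residents.
- **Size.** The share of residents is assumed. Contributor selection may differ by Study Requestor (Table 1 footnote) and reports are Requestor-specific (Section 8.3), so VAHNSI's weight in a given report is not fixed.

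None of this removes the contradiction or the low bias in the share. Reporting by Study Contributor would show VAHNSI's zero, but would not correct the pooled or Spanish figure.

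**Conclusion.** The point holds for the eligibility statement and for the count and share of long-term-care residents. The protocol contradicts itself on who is enrolled at 5 of 22 hospitals, in a group it names and reports, and does not list this as a limitation. Followed as written, the pooled share of residents is about 17–23% too low in relative terms and Spain's about 41–50% too low.

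These ranges rest on three assumptions: equal enrolment per hospital as planned, the same true share at every hospital, and that share lying between 5% and 30%. If enrolment followed beds, the shortfalls would be smaller, about 12–16% pooled and 30–38% in Spain, in the same direction.

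Positivity among residents has no determined direction of bias; it simply does not represent VAHNSI. The residence coding is an inconsistency that may lower the share further. The change should be made, but it does not threaten the main pathogen-positivity objective.

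**What to change.** 1. State the VAHNSI restriction as a site-specific exclusion in Section 3.3.2 and the abstract, and add it to Section 5.
2. Calculate the long-term-care share, pooled and for Spain, without VAHNSI in the denominator: 17 × 270 = 4,590 patients pooled and 5 × 270 = 1,350 in Spain. Say that it describes the remaining hospitals.
3. State that positivity among residents does not represent VAHNSI. No recalculation is needed there.
4. If incidence is calculated, make VAHNSI's numerator and catchment denominator cover the same population, or withhold its incidence in the elderly.
5. Reconcile the Table 3 residence options with the discharge categories. Count prior residence in a nursing home as long-term care unless the case report form defines it otherwise.

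The cost is protocol wording, one derived variable and a smaller denominator for one characteristic. At a share of 10%, the approximate 95% half-width goes from 1.96 × √(0.09/5,940) = 0.76 points to 1.96 × √(0.09/4,590) = 0.87 points, ignoring clustering by hospital. That is small beside the 2.3-point shortfall (10% read as 7.7%) it removes.
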